8.4 Serious Adverse Events

8.4.1 Serious Adverse Event Definition

An event is defined an SAE if it:	Guidance		
results in death	Any event resulting in a fatal outcome must be fully documented and reported, including deaths occurring within 4 weeks after the treatment ends and irrespective of the causal relationship to the IMP. The death of a subject enrolled in a trial is per se not an event, but an outcome.		
is life-threatening	The term life-threatening refers to an AE in which the subject was at immediate risk of death at the time of the event. It does not refer to an event, which may have caused death if it were more severe.		
requires inpatient hospitalization or prolongation of existing hospitalization	The term hospitalization means that the subject was admitted to hospital or that existing hospitalization was extended as a result of an event. Hospitalization describes a period of at least 24 hours. An overnight stay for observation, a stay at an emergency room, or treatment on an outpatient basis does not constitute a hospitalization. However, medical judgment must always be exercised and when in doubt the case should be considered serious (i.e., if the case fulfills the criterion for a medically important event). Hospitalizations for administrative or social purposes do not constitute an SAE. Hospital admissions and/or surgical operations planned before trial inclusion are not considered AEs if the illness or disease existed before the subject was enrolled in the trial, provided that the condition did not deteriorate during the trial.		
results in persistent or significant disability/incapacity	Disability/incapacity means a substantial disruption of a person's ability to conduct normal life functions. If in doubt, the decision should be left to medical judgment by the Investigator.		
is a congenital anomaly/birth defect	Congenital anomaly/birth defect observed in any offspring of the subject conceived during treatment with the IMP.		
is an important medical event	Important medical events are events that may not be immediately life-threatening or result in death or hospitalization but may jeopardize the subject or may require intervention to prevent 1 of the other outcomes listed in the definition above. Examples of important medical events include AEs that suggest a significant hazard, contraindication or precaution, occurrence of malignancy, or development of drug dependency or drug abuse. Medical and scientific judgment should be exercised in deciding whether events qualify as medically important.		
	Important medical events include any suspected transmission of an infectious agent via a medicinal product. Any organism virus or infectious particle (e.g., prion protein transmitting transmissible spongiform encephalopathy), pathogenic or non-pathogenic, is considered an infectious agent. A transmission of an infectious agent may be suspected from clinical symptoms or laboratory findings indicating an infection in a subject exposed to a medicinal product.		

Date: 10 Dec 2015 E-Protocol Amendment-19588; Ver. 1.0 Supersedes: 28 October 2015 Page 48 of 69

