- Ovidrel[®] (choriogonadotropin alfa), manufactured by EMD Serono Inc., will be provided as a pre-filled syringe (0.5 mL) delivering 250 µg choriogonadotropin alfa, to be administered as a single injection as soon as 3 follicles of ≥17 mm are observed on TVUS.
- ENDOMETRIN® (progesterone), manufactured by Ferring Pharmaceuticals Inc., will be

Date: 10 Dec 2015 E-Protocol Amendment-19588; Ver. 1.0 Supersedes: 28 October 2015 Page 6 of 69

provided as inserts to be administered vaginally. On the day that the progesterone inserts are initiated, only a single, 100 mg dose of ENDOMETRIN® will be given. On subsequent days, ENDOMETRIN® will be administered 2 times daily, each delivering 100 mg of progesterone (200 mg/day). ENDOMETRIN® will be initiated the evening of the day after oocyte retrieval and will continue until the day of the second β -hCG test (if negative) or if pregnancy is confirmed by the second β -hCG test for a maximum of 10 weeks total.

DURATION OF TREATMENT

Subjects are treated with IMPs (either HP-hMG or Gonal-f®) for a maximum of 20 days.

Trial Code: 000205

STATISTICAL METHODS

Sample Size Calculation

The study has at least 80% power, with 275 subjects per treatment group, to demonstrate the non-inferiority of MENOPUR® to Gonal-f® in the ongoing clinical pregnancy rate at the 1-sided significance level of 0.025 with a 12% non-inferiority margin, by assuming an ongoing pregnancy rate of 50% for both treatment groups (Yeh et al. 2014). Assuming that 8% of the subjects may not be eligible for the per protocol analysis set, approximately 600 subjects will be randomized (1:1) into this study.

Efficacy:

The primary objective of the trial is to demonstrate the non-inferiority of MENOPUR® versus Gonal-f® with respect to ongoing pregnancy rate in women undergoing COS following a GnRH antagonist protocol. The non-inferiority limit for the difference between treatments (MENOPUR® minus Gonal-f®) will be -12% (absolute). The non-inferiority hypothesis to be tested for the primary endpoint will be:

```
H_0: \pi_{MENOPUR} - \pi_{Gonal-f} \le -12% against the alternative H_1: \pi_{MENOPUR} - \pi_{Gonal-f} > -12%, where
```

 $\pi_{MENOPUR}$ and $\pi_{Gonal-f}$ denote the ongoing pregnancy rate of subjects treated with MENOPUR[®] and Gonal-f[®], respectively, in a single fresh blastocyst transfer following a GnRH antagonist protocol.

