Post-trial follow-up extends to collection of delivery information (live birth and neonatal health to include APGAR scores, birth weight, gestational age at birth, presence of congenital anomaly/birth defect, and cause of neonatal death, if applicable), which will be collected for all subjects with an ongoing pregnancy in the fresh cycle or the 6-month post-randomization frozen-thawed blastocyst transfer cycles. Live birth rate after the fresh cycle and cumulative live birth rate after fresh and 6-month post-randomization frozen-thawed blastocyst transfer cycles will be evaluated as part of the post-trial follow-up.

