3.3.5 Selection and Timing of Dose for Each Subject

The dose of the investigational medicinal product (IMP) (MENOPUR® or Gonal-f®) will be initiated at 150 IU for the first 5 days. From stimulation Day 6 onward, based on follicular response assessed by TVUS, dosing can be adjusted every day, as needed, by 75 IU per adjustment. However, the maximum gonadotropin dose will be 300 IU/day; gonadotropin dosing can continue for a maximum of 20 days.

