6.5 Visit 5 - Oocytes Retrieval/Insemination

A TVUS will be performed and oocytes retrieved roughly 36 hours after hCG administration. Oocytes will be inseminated using partner or donor sperm by ICSI 4±1 hours after retrieval.

Oocyte maturity will be assessed at the time of ICSI. Fertilization (number of pronuclei) will be checked on Day 1 following oocyte retrieval. Embryos must be cultured individually in separate dishes/droplets following the Day 1 assessment. Embryo quality will be assessed on Days 3 and 5 following oocyte retrieval; in the case of late blasulation, assessment will be performed on Day 6 or Day 7, as needed. A standardized embryo grading system will be used and documented in the eCRF. Adverse events and concomitant medications will be assessed and documented.

Each subject will be provided with vaginal progesterone inserts (200 mg/day – ENDOMETRIN[®]) to begin luteal support on the evening of the day after oocyte retrieval. The dose will be administered following the instructions provided in the package insert. Luteal phase support will continue until negative β -hCG (10-14 days after blastocyst transfer) or 8-9 weeks gestation, if pregnant.

Date: 10 Dec 2015 E-Protocol Amendment-19588; Ver. 1.0 Supersedes: 28 October 2015 Page 34 of 69

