6.9 Pregnancy Follow-Up

After confirmation of ongoing pregnancy in the fresh cycle or the 6-month post-treatment frozen-thawed blastocyst transfer cycle, the site will be required to collect delivery information (live birth and neonatal health). The follow-up will be conducted by the study center via telephone or mail and recorded in the eCRF. The site will also document miscarriage/pregnancy loss (spontaneous and/or induced), date of live birth, number of deliveries, gestational age at delivery, birth weight at deliveries, gender, and congenital anomalies/birth defects. Live birth rate after the fresh cycle and

Trial Code: 000205

Date: 10 Dec 2015

E-Protocol Amendment-19588; Ver. 1.0

Supersedes: 28 October 2015

Page 36 of 69

cumulative live birth rate after fresh and 6-month post-treatment frozen-thawed transfer cycles will be evaluated as part of the pregnancy follow-up.

Date: 10 Dec 2015 E-Protocol Amendment-19588; Ver. 1.0 Supersedes: 28 October 2015 Page 37 of 69

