8.5.2 Collection of Serious Adverse Events with Onset after Last Trial

If an Investigator becomes aware of an SAE after the subject's last visit, and he/she assesses the SAE to have a reasonable possible causality to the IMP, the case will have to be reported to Ferring, regardless how long after the end of the trial this takes place.

Date: 10 Dec 2015 E-Protocol Amendment-19588; Ver. 1.0 Supersedes: 28 October 2015 Page 50 of 69

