9.4 Post-Trial Endpoints

All post-trial endpoints will be summarized using tables and figures, as appropriate. Additional details will be specified in the separate Statistical Analysis Plan for the post-trial endpoints. The post-trial endpoints include:

- Cumulative live birth rate for fresh and frozen blastocyst transfer (defined as the proportion of subjects with at least 1 viable live birth greater >21 weeks gestation).
- Live birth rate for fresh blastocyst transfer (defined as the proportion of subjects with at least 1 viable live birth greater >21 weeks gestation).
- Early pregnancy loss rate in frozen blastocyst transfer is defined as 2 positive β -hCG tests but no ongoing pregnancy at 10-11 weeks gestation in the frozen cycle.
- Late pregnancy loss rate (defined as a confirmed ongoing pregnancy but no viable live birth greater >21 weeks gestation).
- Positive β -hCG rate, clinical pregnancy rate, and ongoing pregnancy rate for frozen blastocyst transfers.

Descriptive statistics will be provided for each of the respective post-trial endpoints.

10 Safety

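### The guidance to the birth-defect SAE criterion requires conception during IMP treatment, which no trial embryo can meet, so the reporting duty contradicts itself

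*Protocol*

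**What the plan says.** The SAE table in Protocol 8.4.1 has two columns. The criterion column names congenital anomaly or birth defect with no condition attached. The guidance column reads: "Congenital anomaly/birth defect observed in any offspring of the subject conceived during treatment with the IMP".

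The IMP is only the gonadotropin. Protocol 3.3.5 says "The dose of the investigational medicinal product (IMP) (MENOPUR® or Gonal-f®) will be initiated at 150 IU for the first 5 days", and Protocol 5.1.2 classes ganirelix, Ovidrel and progesterone as non-investigational products. On duration, the synopsis says "Subjects are treated with IMPs (either HP-hMG or Gonal-f®) for a maximum of 20 days". Protocol 6.5 has "oocytes retrieved roughly 36 hours after hCG administration", with ICSI after that.

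Sites must gather offspring outcomes. The delivery information in Protocol 3.1.2 includes "presence of congenital anomaly/birth defect, and cause of neonatal death, if applicable", for pregnancies from fresh and frozen transfers. The list in Protocol 6.9 ends with "gender, and congenital anomalies/birth defects"; it does not mention neonatal death.

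For SAEs that come to light after the last visit, Protocol 8.5.2 makes reporting depend on whether "he/she assesses the SAE to have a reasonable possible causality to the IMP". On analysis, SAP 9.4 says "Descriptive statistics will be provided for each of the respective post-trial endpoints". Neither anomaly nor neonatal death is among the endpoints it lists, and it defers further detail to a separate post-trial SAP.

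**The concern.** The purpose of the treatment under trial is pregnancy, so offspring outcome is a safety matter that the protocol itself names and collects. The one SAE criterion written for that outcome carries guidance that fits a drug taken around natural conception. In IVF the stimulation drug has stopped before any oocyte is fertilized.

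A site that follows the guidance to the letter would record a birth defect on the delivery form and see no duty to send an SAE report. A site that follows the criterion column would see such a duty. The count of congenital-anomaly SAEs would then depend partly on how each site read the table. The trial is open-label and investigators are not among the blinded roles listed in Protocol 3.3.3 and 5.5, so differences in reporting could also differ by arm.

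**Working it through.** There is no planned figure to reproduce. The check is a timeline from the protocol's own intervals, followed by a search of the AE and SAE rules for another route.

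**Step 1: from the last IMP dose to fertilization.** Inputs: the final stimulation day is the trigger day (Protocol 6.3); retrieval is 36 ± 2 h after hCG (Table 1); ICSI is 4 ± 1 h after retrieval (Protocol 6.5).

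- Nominal: 36 + (4 − 1) = 39 h to 36 + (4 + 1) = 41 h after trigger.
- With the retrieval window: (36 − 2) + (4 − 1) = 37 h to (36 + 2) + (4 + 1) = 43 h.
- Limiting case: suppose the last dose came a full 24 h after trigger, later than the protocol allows. ICSI would still follow by at least 37 − 24 = 13 h.

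After a GnRH agonist trigger, retrieval is also about 36 h later (Protocol 3.1.2). A rescue hCG dose can only delay retrieval. Fertilization therefore always follows IMP treatment.

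**Step 2: if conception is dated from transfer instead.** Fresh transfer is on Day 5 after ICSI. A frozen transfer cycle can start up to 6 months after randomization, against at most 20 days of IMP. The interval only lengthens, so neither dating of conception satisfies the guidance.

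**Step 3: from the last visit to birth.** Pregnant subjects have their final visit 8-9 weeks after transfer, at 10-11 weeks' gestation (Protocol 8.3 and 2.2). A counted live birth is beyond 21 weeks.

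- Shortest gap: 21 − 11 = 10 weeks to 21 − 10 = 11 weeks.
- Term birth, assumed at 40 weeks: 40 − 11 = 29 weeks to 40 − 10 = 30 weeks.

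For frozen cycles the gap is longer, because the end-of-trial visit follows the fresh cycle or, for freeze-all subjects, the blastocyst evaluation (Protocol 6.4 and 6.7). Birth defects seen at delivery are thus always learned of after the last visit.

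**Step 4: other rules that could apply.**

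| Place | Rule | Effect on a birth defect found at delivery |
|---|---|---|
| Protocol 8.1 | An AE occurs in a trial subject | A child is not clearly a subject |
| Protocol 8.2.1 | AEs are followed from consent to the last visit | The birth is later |
| Protocol 8.3 | Live birth data and pregnancy loss go to the eCRF | No link to SAE reporting |
| Protocol 8.4.1, other criteria | Death, disability, important medical event | May reach some cases by judgment |
| Protocol 8.5.2 | Later SAEs are reported if judged related | A route, subject to the investigator's judgment |
| SAP 10.2 | Treatment-emergent AEs end at the end-of-trial visit | Outside the AE tables |

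No section says whether an anomaly found at the planned follow-up is to be handled as an SAE.

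**Step 5: scale, for illustration only.** The planning assumption gives 600 × 0.50 = 300 fresh ongoing pregnancies. With an assumed defect prevalence of 2% to 4%, which is not in the documents, that is 300 × 0.02 = 6 to 300 × 0.04 = 12 cases. The calculation treats every ongoing pregnancy as a birth and omits frozen cycles.

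**The case against.** The strongest reply is that the criterion is unqualified and the restriction is only guidance. A site could also read treatment as the treatment cycle; Protocol 9.6.2 itself speaks of a single fresh treatment cycle. This stands, and it sets the limit of the point. A reader might infer that birth defects fall outside SAE reporting altogether, or that the trial would show no such SAEs whatever happened. The documents do not support that. They leave two readings open, and the treatment-cycle reading is unclear for frozen transfers if conception is dated from transfer.

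Second, Protocol 8.5.2 gives a route, with no time limit, for any later SAE judged possibly related, and delivery findings go into the eCRF, whose final database copy goes to the sponsor (Protocol 6.9 and 10.2). So the inference that the sponsor would never assess these cases is too strong. What is missing is an explicit trigger for prompt reporting. Protocol 8.4.2 lets either the investigator or the sponsor judge causality, but under 8.5.2 a late case needs the investigator's judgment before any report is required.

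Third, a reader might infer that anomalies will never be compared by arm. That cannot be shown. Protocol section 9 and SAP 9.4 defer post-trial analyses to a separate SAP that was not available, and it may include such a table. What can be shown is that neither document lists these outcomes as endpoints.

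Last, requiring a report within 24 hours whatever the causality judgment would be partly a preference. Nothing in the documents demands it, and the rewording of 8.4.1 does not depend on it.

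**Conclusion.** The point holds as an internal contradiction in a safety-reporting rule. Taken literally, the guidance in Protocol 8.4.1 applies to no child of the trial, while the criterion beside it applies to all of them. This rests only on the protocol's own timing and on the IMP being the gonadotropin alone.

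The practical effect is an unclear duty that sites may apply inconsistently. It is compounded because births come at least about 10 weeks after the last visit, when only events judged related must be reported. The number of children affected cannot be derived from the documents; the 6 to 12 above is illustrative and the conclusion does not need it. The primary endpoint and its analysis are untouched. The correction should be made because it is cheap and concerns an outcome the protocol already requires sites to collect.

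**What to change.** 1. In the guidance of Protocol 8.4.1, replace the closing condition (everything after the word *subject*) with: *conceived from oocytes retrieved in the trial stimulation cycle, by fresh or frozen transfer*.
2. Reconcile Protocol 3.1.2, 6.9, 8.2.1, 8.3, 8.4.1 and 8.5.2 so that the protocol states whether, how and by when an anomaly found at the planned delivery follow-up enters SAE reporting, and whether the investigator's causality judgment is a condition. Align 6.9 with 3.1.2 on neonatal death.
3. Name congenital anomaly and neonatal death, by arm, among the outcomes for the separate post-trial SAP. Counting per child born is a natural denominator.

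The first change stands on its own if the others are deferred. The cost is protocol wording, one table and a handful of additional SAE reports. The delivery information is already to be collected, although 6.9 must be aligned for neonatal death.

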8.4.2 Collection, Recording and Reporting of Serious Adverse Events

SAE Reporting by the Investigator

All SAEs must be reported immediately to the contract research organization (CRO) and/or Ferring Pharmaceuticals as soon as it becomes known to the Investigator and not later than within 24 hours of their knowledge of the occurrence of an SAE.

The Investigator is responsible for submitting the completed SAE Report Form with the fullest possible details to the CRO and/or the local safety officer at Ferring Pharmaceuticals, Inc. by fax within 24 hours of his/her knowledge of the SAE and submit all related follow-up information no later than 3 calendar days using the contact details below:

Completion of the Demographics Log, AE Log, Medical History Log, and Concomitant Medication Log is mandatory for initial reports and for follow-up reports if any changes have been made since the initial report.

Additional information relevant to the SAE such as hospital records, results from investigations, e.g., laboratory parameters (that are not already uploaded in the eCRF), invasive procedures, scans and x-rays, and autopsy results can be faxed or scanned and e-mailed to Ferring Pharmacovigilance using the contact details in the section above. In any case, this information must be supplied by the Investigator upon request from Ferring. On any copies provided, details such as the subject's name, address, and hospital identification number should be concealed and instead the subject number should be provided.

The Investigator will supply Ferring and the IRB with any additional requested information, such as results of post-mortem examinations and hospital records.

Expedited Reporting by Ferring

Ferring will report all AEs that are serious, unexpected, and with a reasonable possible causality to the IMP, as judged by either the Investigator or Ferring, to the relevant parties within the stipulated timelines.

The expectedness is assessed by Ferring according to the Package Inserts for both the IMP and Non IMP products.

Serious AEs will be considered reportable regardless of whether or not the IMP or Non IMP was used in accordance with the provisions in the protocol, Package Inserts, and labeling.

Date: 10 Dec 2015 E-Protocol Amendment-19588; Ver. 1.0 Supersedes: 28 October 2015 Page 49 of 69

8.5 Follow-up of Adverse Events and Serious Adverse Events

8.5.1 Follow-up of Adverse Events with Onset during the Trial

During the trial, the Investigator must follow-up on each AE until it is resolved or until the medical condition of the subject is stable.

Trial Code: 000205

After the subject's last visit, the Investigator must follow-up on any AE classified as serious or considered to have a reasonable possible causality to the IMP until it is resolved or until the medical condition of the subject is stable. All such relevant follow-up information must be reported to Ferring. If the event is a chronic condition, the Investigator and Ferring may agree that further follow-up is not required.

8.5.2 Collection of Serious Adverse Events with Onset after Last Trial

If an Investigator becomes aware of an SAE after the subject's last visit, and he/she assesses the SAE to have a reasonable possible causality to the IMP, the case will have to be reported to Ferring, regardless how long after the end of the trial this takes place.

Date: 10 Dec 2015 E-Protocol Amendment-19588; Ver. 1.0 Supersedes: 28 October 2015 Page 50 of 69

9 STATISTICAL METHODS

This section details the planned statistical analyses for the primary endpoint and outlines the secondary endpoints. All analyses and further descriptions of the statistical methodology for the primary and secondary endpoints will be included in the Statistical Analysis Plan available before the first subject signs their informed consent. Any deviations from the protocol-specified statistical analysis will be described in the Statistical Analysis Plan or final report, as appropriate. A separate Statistical Analysis Plan will be prepared to cover the post-trial information.

9.1 Determination of Sample Size

The study has at least 80% power, with 275 subjects per treatment group, to demonstrate the non-inferiority of MENOPUR® to Gonal-f® in the ongoing clinical pregnancy rate at the 1-sided significance level of 0.025 with a 12% non-inferiority margin, by assuming an ongoing pregnancy rate of 50% for both treatment groups (Yeh et al. 2014). Assuming that 8% of the subjects may not be eligible for the PP analysis set, approximately 600 subjects will be randomized (1:1) into this study.

